**AN INVESTIGATION INTO THE RELATIONSHIP BETWEEN HEMORRHOID
DISEASE AND THE USE OF SMARTPHONES IN THE LAVATORY**

Unique Protocol ID: 12/22/2017 – 051

Date: February 11, 2018

Statistical Analysis

All data will be analyzed using the SPSS package program (version 20). The data will consist of categorical, nominal, and continuous numerical variables. Frequency and percentage rates will be given for categorical and nominal variables. Following testing for normal distribution, variables with normal distribution will be expressed as mean \pm standard deviation, while those that do not exhibit normal distribution will be expressed as median and minimum – maximum values. The relationship between risk factor and outcome variable will be evaluated using the Chi-square test. The effect of smartphone use on the presence or absence of hemorrhoids will be analyzed using the Binary Logistic Regression method. Any difference in the degree of hemorrhoids with respect to the duration of exposure to the risk factors will be determined by ANOVA or the Kruskal-Wallis test. A *p*-value of less than .05 will be considered statistically significant.

Calculation of Sample Size

According to the results of the pilot study, 36.4% of the population with hemorrhoidal disease use a smartphone for at least 2 minutes while in the lavatory. In the control group, this percentage was only 13.2%. Since this is a case-control study, the investigators first calculated the number of cases required to calculate the prevalence of a group with hemorrhoidal disease as per the below:

$$n = \frac{Z^2 p(1-p)}{d^2} \quad n = \frac{1.96^2 * 0.364(1-0.364)}{0.05^2} \quad N = 355.7$$

According to the above, in order to estimate a 5% difference in effect size, with an error rate of 5% and 80% power, at least 356 patients are needed. However, in this study, the sample for the logistic regression analysis needs to be calculated in order to investigate to what extent the use of a smartphone during defecation increases the risk of hemorrhoids.

According to analyses performed using the pilot study data, the percentage of the whole population who use a smartphone for at least 2 minutes while in the lavatory is 26.9%. In the logistic regression analysis, in order to determine whether or not smartphone use during defecation (the independent variable) has an effect on the presence or absence of hemorrhoidal disease (the dependent variable), the approach suggested by Peduzzi et al. (1) is as per the below:

$$N = 10 k / p$$

where

P = the rate of positive or negative events in the population

K = the number of independent variables.

$$N = 10 * (22 / 0.269) = 817.8$$

According to these calculations, calculating the prevalence of smartphone use in the lavatory among the hemorrhoid patient population and measuring the effect of this habit on hemorrhoid development requires 818 patients and the same number of controls. Taking into account the possibility for incomplete or incorrect questionnaires by adding 10% loss to this figure results in a total of $818 + 81 = 899$ participants needed.

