**AN INVESTIGATION INTO THE RELATIONSHIP BETWEEN HEMORRHOID
DISEASE AND THE USE OF SMARTPHONES IN THE LAVATORY**

Unique Protocol ID: 12/22/2017 – 051

Date: February 11, 2018

Tarih :
Versiyon :

STUDY PROTOCOL

The objective of medical research: A changing world not only brings about different lifestyles and diverse eating habits, it also changes the causes and courses of known diseases. The goal of this study is to examine the relationship between hemorrhoids, a common complaint, and the use of smartphones, also a common feature of modern life, in the lavatory.

The scientific basis and validity of medical research: As is known, hemorrhoidal disease is a frequently observed disease of the lower rectum and anal region that seriously impairs the patient's quality of life. Its worldwide prevalence is reported to be approximately 4.4% [1, 2]. One out of every two people over the age of 50 is reported to experience symptomatic hemorrhoidal disease, with increased frequency with age, especially after the age of 45 [3].

The underlying physiopathological event is vascular enlargement of the lower rectum [2]. Hemorrhoids are classified as internal or external, and it is assumed that the same pathological mechanisms operate in both types (**Figure 1**). Accepted pathological mechanisms and predisposing factors are summarized as follows:

Reduced venous drainage

Many researchers believe that foods low in fiber reduce stool caliber and cause an increase in straining during defecation, thereby increasing the pressure on the anal region [4]. The increased pressure in the anal region leads to prolapsed hemorrhoids and at the same time inhibits venous return. The inhibition of venous return further increases the prolapse of hemorrhoids thus rendering it symptomatic. Hemorrhoids may also develop via the aforementioned mechanism in situations where pressure is augmented such as pregnancy and increased anal sphincter tone. Sitting on the toilet for a long time (for example, while reading a newspaper) has been determined to inhibit venous drainage (the tourniquet effect) [5]. Together with aging, the weakening-loosening of the connective tissue supporting hemorrhoid papillae accelerates the development of hemorrhoidal disease.

Straining and constipation

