The study population consists of patients with complaints of hemorrhoids referred to the General Surgery Polyclinic. The control group is comprised of healthy volunteers with no complaints of hemorrhoids (Figure 3). Both the study group and the control group will include persons of both genders between 16 and 65 years of age. Informed consent will be obtained from patients and volunteers, following which a Likert-type survey will be given to each participant to complete (Table 1, questionnaire form). A pilot study will be conducted for the factor analysis of the questions to be asked in the questionnaire. In the pilot study, the target will be to survey 100 patients. After the factor analysis is performed on 100 patients, the questionnaire that is developed will be used in the main study.

As no prevalence study was previously performed for the sample size, it will be calculated based on the prevalence (frequency of smartphone use in the lavatory in the study group and the control group) determined after the pilot study, accepting a type I error of 0.005 and a type II error of 0.20 (80% test power).

The doctor who performs the examinations will be blinded to the questionnaire results. After completion of the questionnaire, the patient's anal region and rectum will be examined by a general surgeon and the presence or absence of hemorrhoids will be noted. Subsequently, if hemorrhoids are present, they will be recorded as either external or internal. Internal hemorrhoids will then be staged as first-degree, second-degree, third-degree, or fourth-degree, according to standard textbook definitions [2].

Primary endpoints of the study:

1) determination of the stage of hemorrhoids in patients with complaints of hemorrhoids

Tarih :

Versiyon :

2) frequency and duration of smartphone use in the lavatory for those with smartphones

Statistical Data Analysis:

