All data will be analyzed using the SPSS version 20 package program. The data will consist of categorical nominal and continuous numerical variables. Frequency and percentages will be given for categorical and nominal variables. Following testing for normal distribution of numerical variables, those with normal distribution will be expressed as mean \pm standard deviation, while variables without normal distribution will be expressed as median value and minimum - maximum. The relationship between the risk factor and the outcome variable will be assessed using the Chi-square test. The difference between hemorrhoid stages in terms of exposure times to the risk factor will be determined by ANOVA or the Kruskal-Wallis test. A *p* value of 0.05 will be accepted as statistically significant.

Tarih :

Versiyon :

REFERENCES

2. Lowney JK, Fleshman JW Jr. Benign disorders of the anorectum (pelvic floor, fissures, hemorrhoids, and fistulas). In: Zinner MJ, Ashley SW, eds. *Maingot's Abdominal Operations*. 11th ed. New York: McGraw-Hill; 2007: 663-693.
7. Wald A. Constipation, diarrhea, and symptomatic hemorrhoids during pregnancy. *Gastroenterol Clin North Am*. 2003; 32: 309-322, vii.
10. Bernstein WC. What Are Hemorrhoids and What Is Their Relationship to the Portal Venous System. *Diseases of the Colon & Rectum*. 1983; 26: 829-834.

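### The only planned test of hemorrhoid degree against phone duration is unadjusted; if degree rises and duration falls with age, it can show a false inverse relation or hide a true one

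*SAP*

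**What the plan says.** Both documents relate severity to exposure in one sentence each. The protocol (Statistical Data Analysis) has: "The difference between hemorrhoid stages in terms of exposure times to the risk factor will be determined by ANOVA or the Kruskal-Wallis test". The SAP (Statistical Analysis) has: "Any difference in the degree of hemorrhoids with respect to the duration of exposure to the risk factors will be determined by ANOVA", with Kruskal-Wallis as the alternative. Neither names a covariate, a stratum or a model that uses the ordering of the degrees.

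The plan's one multivariable model has a different outcome: "The effect of smartphone use on the presence or absence of hemorrhoids will be analyzed using the Binary Logistic Regression method". The 22 independent variables in the sample size section belong to that model and are not listed.

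The protocol's two primary endpoints are "determination of the stage of hemorrhoids in patients with complaints of hemorrhoids" and "frequency and duration of smartphone use in the lavatory for those with smartphones". The degree-by-duration test is the only planned analysis that joins them.

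On age, the protocol's background says the disease occurs "with increased frequency with age, especially after the age of 45", and that with aging "the weakening-loosening of the connective tissue supporting hemorrhoid papillae accelerates the development of hemorrhoidal disease". Patients and controls are enrolled from 16 to 65 years. The stated protection against confounding is that the study and control groups resemble each other.

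**The concern.** One-way ANOVA and Kruskal-Wallis, as planned, cannot hold age constant. Degree is compared among patients, so the control group plays no part, and even perfectly matched controls would leave confounding within the patient group untouched.

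Age is the obvious candidate because the protocol itself ties it to the disease and the enrolled range is wide. If older patients have higher degrees and shorter phone times, the unadjusted comparison mixes the effect of age with any effect of phone use. Longer use could then appear to go with milder disease when there is no effect, or a real positive relation could be cancelled. This is the plan's only dose-severity evidence.

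**Working it through.** **The plan's own figures.** Precision formula: 1.96² × 0.364 × 0.636 / 0.05² = 355.7, rounded up to 356. Events-per-variable rule: 10 × 22 / 0.269 = 817.8, rounded up to 818. Both reproduce. Neither was set for the degree test, for which no sample size or power is given.

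**Inputs from the documents.** Ages 16 to 65; significance level .05; 818 patients. Because only internal hemorrhoids are graded, and the SAP asks for 818 patients plus as many controls but then totals 818 + 81 = 899, half that number (818 / 2 = 409) was also run.

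**Assumed inputs.** Age uniform over the range; four degrees with shares 30/30/25/15%; latent degree correlated +r with age; log duration correlated −r with age; no link between degree and duration at a given age. The documents give none of these, so r is varied.

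**Mechanism.** With no true effect, the correlation induced between latent degree and log duration is −r × r: −0.01, −0.04, −0.09 and −0.16 for r = 0.1, 0.2, 0.3 and 0.4.

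**Simulation, 1,000 runs per setting.** The table shows the share of runs with p < .05.

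| r | Mean Spearman (818) | Kruskal-Wallis, 818 | Age-adjusted, 818 | Kruskal-Wallis, 409 |
|---|---|---|---|---|
| 0.1 | −0.011 | 5% | 5% | 5% |
| 0.2 | −0.037 | 12% | 5% | 8% |
| 0.3 | −0.083 | 50% | 5% | 28% |
| 0.4 | −0.149 | 97% | 6% | 73% |

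The Monte Carlo standard error is at most √(0.5 × 0.5 / 1000) = 1.6 percentage points. Repeat runs gave about 95% at r = 0.4 with 818 patients, and about 26% and 74% at r = 0.3 and 0.4 with 409. With 818 patients, nearly all significant results from r = 0.2 upward are inverse. If one correlation is 0.3 and the other zero, the rate is 4 to 6%. The age adjustment checked here was an analysis of covariance of log duration on degree and age.

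**Hand check.** Four groups give 3 degrees of freedom and a critical value of 7.81. The noncentrality is roughly n × (Spearman)². For 818 patients: 818 × 0.037² = 1.12, 818 × 0.083² = 5.64 and 818 × 0.149² = 18.16. The noncentral chi-square then gives 12%, 49% and 96%, in agreement with the simulation.

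**Masking.** Take r = 0.3 and a true effect of 0.1 SD of latent degree per SD of log duration. The unadjusted relation is about −0.3 × 0.3 + 0.1 = 0.01, almost nothing. With 818 patients, the planned test is significant in 7% of runs and the age-adjusted test in 61%.

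**Non-users.** A second simulation let age lower the chance of using a phone, raised degree with age, and counted non-users as zero minutes. With log-odds per SD of age of 0.5 and 0.3, 0.8 and 0.4, and 1.0 and 0.5 (use and degree respectively), Kruskal-Wallis was significant in 12%, 37% and 73% of runs with 818 patients. In a rebuild of that model, restricting the test to users brought the rate to 4 to 6% in every setting, because minutes among users did not depend on age. Whether non-users enter the test therefore matters, and neither document says.

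**The case against.** The strongest reply is that the documents establish neither link. The background ties age to the frequency and development of hemorrhoidal disease, which is not the same as degree among referred patients. Nothing ties age to phone duration; the protocol says only that some people have the habit. A reader might infer that age does drive both variables and that the planned test will give a false inverse result. The documents do not support that: both the existence and the direction of the bias rest on assumptions, and with correlations near 0.1 there is no practical problem. This part of the objection stands.

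It also stands that the induced correlation is weak (Spearman about −0.04 at r = 0.2 and −0.08 at r = 0.3), that both planned tests are unordered, so any direction would be read from group means or medians, and that the association of stage with duration is not itself listed as an endpoint. The main risk question rests on the logistic model. Age is also not the only possible confounder: the protocol lists low-fiber diet, constipation, pregnancy and obesity among others.

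None of this answers the core point. The analysis is unadjusted, no other planned analysis covers degree, and the stated safeguard does not act within patients. The sponsor need not know the correlations to adjust for age.

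**Conclusion.** The point holds as a conditional risk. The lack of adjustment is plain from both documents; the size of the resulting error is not known. With 818 graded patients and no true effect, the planned test is significant in about 5% of trials if either age correlation is zero or both are 0.1, about 12% at 0.2, 50% at 0.3 and 95% at 0.4. With about 409 the rates are about 5%, 8%, 26 to 28% and 73 to 74%. Age adjustment brings the rate back to about 5%.

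These are false positives for an effect of phone use. The test would be detecting a real unadjusted association that age produces. The figures rest on the assumed correlations, degree shares and age distribution. This is a cheap improvement to the plan; the documents do not show that the degree result will be wrong.

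**What to change.** In the SAP, make the degree analysis an ordinal (proportional-odds) logistic regression among graded patients, with degree as the outcome, phone duration as the exposure, and age and sex as covariates. Report the odds ratio with its 95% CI. State whether patients who do not use a phone in the lavatory enter as zero minutes; one option is a user indicator plus duration among users, which avoids forcing a single linear effect across the zeros. Keep ANOVA or Kruskal-Wallis as an unadjusted description.

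The cost is a short SAP change and one more model. Age has to be known for eligibility, so no new visit or measurement is needed for it. The model also uses the ordering of the degrees, which the planned tests ignore. The downside is a proportional-odds assumption that must be checked.

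### No named test relates duration or frequency of phone use to having hemorrhoids, and the only exposure definition is an unexplained 2-minute cut

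*SAP*

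**What the plan says.** - **Question.** The protocol's scientific-basis section closes by asking how far smartphones lengthen lavatory time and whether that extra time is associated with hemorrhoidal disease. The mechanism it offers is prolonged sitting, with more straining and impaired venous drainage.
- **Endpoint.** The second of two items under Primary endpoints is "frequency and duration of smartphone use in the lavatory for those with smartphones".
- **Association test.** SAP, Statistical Analysis: "The relationship between risk factor and outcome variable will be evaluated using the Chi-square test". The protocol has an equivalent sentence. Neither defines the categories of the risk factor.
- **Logistic regression.** The SAP adds a binary logistic regression of hemorrhoids (present or absent) on smartphone use, without units or coding.
- **Duration.** Both documents compare exposure time across hemorrhoid stages or degrees by ANOVA or Kruskal-Wallis. No other named test uses duration.
- **The cut.** It appears only in SAP, Calculation of Sample Size, where the pilot share who "use a smartphone for at least 2 minutes while in the lavatory" is given as 36.4% of cases, 13.2% of controls and 26.9% overall. The protocol had said the sample size would rest on the "frequency of smartphone use in the lavatory in the study group and the control group" found in the pilot, and gave no minute threshold.

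**The concern.** The stated question needs an analysis of time against disease status, and the plan names none. The comparison across degrees does not fill the gap. The protocol assigns degrees only to internal hemorrhoids, so as written that test does not set cases against controls.

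The case-control tests are then left with an exposure that is either undefined or, if the sample-size section is the guide, cut at 2 minutes. Such a cut gives one odds ratio for everyone above it. It cannot show whether risk rises with time, which is among the more persuasive evidence an observational design can offer for the proposed mechanism.

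No reason is given for 2 minutes, and the figure appears only beside pilot results. A reader cannot tell whether it was chosen before or after those results were seen. With the coding left open, a threshold could also be chosen from the main-study data.

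**Working it through.** **Which test uses which form of exposure**

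| Analysis | Exposure as written | Compared across |
|---|---|---|
| Chi-square (protocol, SAP) | risk factor, categories not given | outcome variable |
| Logistic regression (SAP) | smartphone use, coding not given | hemorrhoids present or absent |
| ANOVA or Kruskal-Wallis (protocol, SAP) | duration | stages or degrees |
| Frequency of use | no named test | none |

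**The plan's own figures reproduce**

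Inputs, all from SAP, Calculation of Sample Size: 36.4% of cases, 13.2% of controls and 26.9% overall at 2 minutes or more; 22 independent variables.

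- Prevalence: 1.96² × 0.364 × 0.636 / 0.05² = 355.7, so 356.
- Logistic regression: 10 × 22 / 0.269 = 817.8, so 818.

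The 2-minute share is therefore the figure that sizes the logistic regression.

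**Power of a yes/no comparison at the pilot contrast**

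- Odds ratio: (0.364/0.636) / (0.132/0.868) = 3.76.
- Mean proportion (0.364 + 0.132)/2 = 0.248. Pooled term √(2 × 0.248 × 0.752) = 0.611. Unpooled term √(0.364 × 0.636 + 0.132 × 0.868) = 0.588.
- For 80% power at two-sided 0.05: n = (1.960 × 0.611 + 0.842 × 0.588)² / 0.232² = 53.2, so 54 per group. At the protocol's sample-size alpha of 0.005 it is 91.
- At 356 per group: (0.232 × √356 − 1.960 × 0.611) / 0.588 = 5.4, so power is above 99.99%. It also exceeds 99.99% at alpha 0.005 and at 818 per group.

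**Information lost by the cut**

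The documents give no distribution of duration, so the shape is an assumption. For a modest linear effect, the share of trend information kept by a yes/no version is the squared correlation between exposure X and the indicator X > c. For a normal X with a proportion p above the cut, this is φ(c)² / [p(1 − p)].

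- p = 0.269: c = 0.616, φ(c) = 0.330, and 0.330² / (0.269 × 0.731) = 0.554. So 55% is kept and 45% lost.
- Other shapes, simulated with 26.9% above the cut:

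| Assumed shape | Kept | Lost |
|---|---|---|
| Lognormal, sigma 1 | 43% | 57% |
| Normal | 55% | 45% |
| Uniform | 59% | 41% |
| Lognormal, sigma 0.5 | 61% | 39% |
| Exponential | 63% | 37% |

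- With a spike at zero: assume 50% to 70% non-users, exponential or lognormal (sigma 0.5 or 1) minutes among users, and 26.9% at or above the cut. Simulation then gives 64% to 90% kept on a log(1 + minutes) scale and 32% to 74% on raw minutes.

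**The same contrast on both scales**

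If 36.4% against 13.2% arose from a shift in a normal exposure, the shift is −0.348 − (−1.117) = 0.769 SD. For 80% power at two-sided 0.05, 2 × (1.960 + 0.842)² / 0.769² = 26.5, so 27 per group on the continuous scale against 54 on the yes/no scale. Both are far below the planned numbers.

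**The case against.** **Yes/no coding is not in the text.** A reader might infer from "whether or not smartphone use during defecation (the independent variable) has an effect on the presence or absence of hemorrhoidal disease" that the model takes a yes/no exposure. It does not say so: the opening words attach to having an effect, not to the coding of smartphone use. The 2-minute cut stands only in the sample-size section. A Chi-square test can have more than two categories, and a logistic model can take minutes directly. The SAP mentions continuous variables and allows for 22 predictors without listing them, so duration or frequency could be among them. This stands. Binary coding is a reasonable inference, because the 2-minute share sizes the model, but it remains an inference. If it is wrong, the exposure in the main model is undefined and the remedy is the same.

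**Power is not at risk.** A reader might infer a serious loss, since a test with 80% power on a normal exposure falls to about 55% when 45% of the information goes. That is correct arithmetic for a test that starts at 80%. It does not describe this study, whose power at the pilot contrast is above 99.99%. The loss could matter only for much smaller or adjusted effects.

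**Dose is not ignored.** Duration is compared across degrees, which is an exposure-severity analysis, and frequency and duration are one of two primary endpoints, not the only one. Both points are correct. Neither supplies a test of duration against having the disease.

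**The cut's absence from the protocol is weak evidence.** The protocol deferred sample-size inputs to the pilot, so a pilot-based definition first seen in the SAP is expected. That stands; the missing rationale is the issue.

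**Conclusion.** The concern holds as a gap in the planned analysis. The study asks about time and makes frequency and duration a primary endpoint, but names no test of either against presence of hemorrhoids. Exposure coding in both case-control tests is unstated, and the only definition offered is an unexplained 2-minute cut.

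If that cut is the exposure, the comparison cannot show a dose-response. It gives up 45% of the linear-trend information under a normal exposure, and about 37% to 57% over the five shapes tried. With many non-users at zero the loss could be smaller or larger: 10% to 36% on the log scale and 26% to 68% on raw minutes under the assumptions above. These are illustrations, because the documents give no duration data. They do not support a claim that the study is underpowered at its pilot effect, or that the SAP prescribes a yes/no exposure.

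The plan can run without the change, but its named tests would leave its own question about time unanswered. It should be changed.

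**What to change.** In SAP, Statistical Analysis, name the exposure variable for each test.

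- In the logistic regression of hemorrhoids present or absent, enter duration of phone use per visit, with zero for non-users, as a continuous term: for example a spline or log(1 + minutes), with a user/non-user indicator if zeros are many. A plain log will not do, because it is undefined at zero.
- If the questionnaire records only bands, use ordered categories with a trend test.
- Add frequency of use as a further term.
- The endpoint is limited to people with smartphones, so say whether people without one count as zero or are left out.
- Keep at least 2 minutes as a secondary descriptive contrast. Give its rationale and say whether it was set before the pilot results were seen.
- Fix all of this before main-study data are seen.

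The cost is mainly SAP wording, since frequency and duration are already endpoints. Whether minutes are recorded as numbers depends on the questionnaire; hence the banded alternative. If the new terms are not already among the 22, the SAP's own rule adds 10 / 0.269 = 37.2 to the sample size for each. An odds ratio per unit of time is slightly harder to explain, which the secondary contrast covers.

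### The SAP attaches 80% power to 356 patients, but that number comes from a one-prevalence precision formula with no power term

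*SAP*

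**What the plan says.** The SAP, under Calculation of Sample Size, reports from the pilot that "36.4% of the population with hemorrhoidal disease use a smartphone for at least 2 minutes while in the lavatory" and gives 13.2% for controls. It introduces its first calculation as the number of cases needed to determine prevalence in the hemorrhoid group, and enters Z = 1.96, p = 0.364 and d = 0.05 to obtain 355.7. The next sentence describes the result differently: "in order to estimate a 5% difference in effect size, with an error rate of 5% and 80% power, at least 356 patients" are needed.

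The SAP then moves on: "However, in this study, the sample for the logistic regression analysis needs to be calculated". It applies N = 10k/p with 22 variables and p = 0.269, obtains 817.8, and concludes that the study "requires 818 patients and the same number of controls". Adding 10% for loss, it gives 899 participants in total.

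The protocol, under Study protocol, methods, and procedures, had said of the sample size that "it will be calculated based on the prevalence (frequency of smartphone use in the lavatory in the study group and the control group") found in the pilot, "accepting a type I error of 0.005 and a type II error of 0.20 (80% test power"). Its Statistical Data Analysis section says that a *p* "value of 0.05 will be accepted as statistically significant", and the SAP also tests at 0.05.

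**The concern.** A precision calculation and a power calculation answer different questions. The first fixes the width of a confidence interval around one proportion. The second fixes the chance of detecting a stated difference and needs a type II error term, plus a second group if two groups are compared. The SAP uses the first and describes it as the second.

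The sentence matters because no other sentence in the SAP mentions power. If it is wrong, the 80% power promised in the protocol has no supporting calculation for the case-control comparison. A reader would also take it that a 5-point difference is detectable with 356 patients, and could not learn the smallest association that the final sample can detect.

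**Working it through.** **Inputs.** Exposure is 0.364 in cases and 0.132 in controls, d = 0.05, Z = 1.96, and the size is 818 or 899 (all from the SAP, Calculation of Sample Size). Alpha is 0.05 (SAP, Statistical Analysis; protocol, Statistical Data Analysis) or 0.005 (protocol, sample size paragraph). Power is 80%. The documents do not state sidedness; Z = 1.96 implies two-sided 5%, so tests are two-sided unless noted. Normal approximations are used without continuity correction.

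**1. The SAP's figure.** 1.96² × 0.364 × 0.636 / 0.05² = 355.74, rounded up to 356. Back-check: 1.96 × √(0.364 × 0.636 / 356) = 0.04998. So 356 is exactly the size for a half-width of ±5 points.

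**2. One-sample power for a 5-point shift.** The standard error at 356 is √(0.364 × 0.636 / 356) = 0.0255, so 0.05 is 1.96 standard errors. Power = Φ(1.96 − 1.96) = 50% two-sided, or Φ(1.96 − 1.645) = 62% one-sided. For 80% power, (1.96 + 0.8416)² × 0.364 × 0.636 / 0.05² = 726.8, so 727. With separate variances under the null and the alternative, the figure is 712 (shift down) or 738 (shift up). The smallest variant tried, one-sided and downward, needs 559.

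**3. Two-group power for a 5-point difference.** The SAP describes no such test at 356; this asks whether any two-group reading would support the claim. With p̄ the mean of p1 and p2,

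n per group = [z(1−α/2)√(2p̄(1−p̄)) + z(0.80)√(p1(1−p1) + p2(1−p2))]² / (p1 − p2)².

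| Comparison | Power at 356 per group | n per group for 80% |
|---|---|---|
| 36.4% vs 41.4% | 28% | 1,492 |
| 36.4% vs 31.4% | 29% | 1,406 |
| 13.2% vs 18.2% | 45% | 830 |

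**4. The final-size rule.** 10 × 22 / 0.269 = 817.8. This formula has no alpha, no effect size and no power.

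**5. The comparison the protocol promised.** For 36.4% vs 13.2%, p̄ = 0.248, √(2p̄(1−p̄)) = 0.6107, √(0.364 × 0.636 + 0.132 × 0.868) = 0.5883, and the squared difference is 0.232² = 0.0538.
- Alpha 0.05: (1.960 × 0.6107 + 0.8416 × 0.5883)² / 0.0538 = 53.2, so 54 per group.
- Alpha 0.005: (2.807 × 0.6107 + 0.8416 × 0.5883)² / 0.0538 = 90.7, so 91 per group.

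The pilot odds ratio is (0.364/0.636) / (0.132/0.868) = 3.76. At that effect, crude power exceeds 99.9% with 405 or 818 per group, at either alpha.

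**6. Detectable association at the final size.** This solves the formula in step 3 for p1, with control exposure 13.2% and 80% power. If 899 is the total with 10% lost, 899 × 0.9 / 2 = 404.6, about 405 per group.

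| Evaluable per group | Alpha 0.05: p1, odds ratio | Alpha 0.005: p1, odds ratio |
|---|---|---|
| 405 | 20.6%, 1.70 | 23.1%, 1.97 |
| 818 | 18.2%, 1.47 | 19.9%, 1.63 |

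These are crude odds ratios. Adjustment for the other variables in the model is not included.

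**The case against.** The strongest reply is that the sentence decides nothing. The arithmetic is correct, the formula is introduced correctly, and 356 is set aside in the same paragraph. At the pilot contrast even 356 per group has crude power above 99.9% at either alpha. On this view the fault is a wording slip. Most of that stands: this is a fault of documentation, and the shortfall in power applies to the 5-point difference that the sentence names, not to the pilot difference. It does not answer the point that the sentence is in the current SAP, is its only statement about power, and is false.

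A second reply is that 54 or 91 per group would mislead as a justification, because they take a small pilot at face value. This has force. The documents give no pilot counts, but 20/55, 5/38 and 25/93 would reproduce 36.4%, 13.2% and 26.9%. If those were the counts, the odds ratio would be 3.77 with a 95% interval of about 1.27 to 11.2. At 1.27, power would be only about 22% with 405 per group and 40% with 818. So the promised calculation should be shown for completeness, but the detectable odds ratio is the figure that informs.

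A third reply is that deducting 10% from 899 is not the SAP's own accounting, which adds 10% to 818. Taking 818 evaluable in total gives 409 per group, and the odds ratios become 1.70 and 1.96. Nothing changes.

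Finally, the two alphas and the ambiguous final size are separate faults. That is so, but a correct power statement cannot be written until both are settled.

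**Conclusion.** The concern holds. The number 356 is a precision size for one prevalence, and 80% power for a 5-point difference does not follow from it under any reading tried: about 50% in one sample (62% one-sided), and 28% to 45% with 356 per group. Neither document contains a calculation that supports 80% power for the case-control comparison.

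This does not show an underpowered study. If the pilot rates are right, either reading of the final size is far more than enough. If a 5-point difference around 36.4% were truly the target, even 818 per group would give only 55% to 57% power at alpha 0.05. From a 13.2% baseline, 818 falls just short of the 830 needed.

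These results rest on two-sided tests, equal groups, normal approximations and no covariate adjustment. The point should be fixed, and confidence in it is high.

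**What to change.** In the SAP, Calculation of Sample Size:

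1. State that 356 cases estimate the prevalence of lavatory smartphone use among cases with a 95% confidence interval half-width of ±5 percentage points. Delete the references to 80% power and to an effect size.
2. Choose one alpha, 0.005 or 0.05, and use it in both documents for planning and testing.
3. Add the comparison the protocol promised (36.4% vs 13.2%, 80% power, two-sided, no continuity correction): 91 per group at 0.005, or 54 at 0.05. Say that it relies on the pilot estimates.
4. State whether the final size is 899 in total, or 818 patients plus as many controls. Give the crude detectable odds ratio for that size: about 1.70 or 1.47 at 0.05, or about 1.97 or 1.63 at 0.005. Note that covariate adjustment is not included.

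The cost is a few sentences and one short calculation. No extra patients are needed.
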